The intervention phase of Phase I and II parts of the study will be followed by an open-label extension phase that will begin after the assessment on Day 29. Assessments of fatigue, physical activity, and psychosocial functioning will be conducted at baseline, day 15 and day 29. On Day 29, the study will be completed and patients will be given the option of continuing on an open label basis, Panax ginseng 800 mg per day, will be provided they have tolerated the double-blind phase without moderate to severe toxicity as per NCI CTC AE V4 criteria. All patients will be taken off the study on day 57. Patients will be followed for upto 30 days after the last dose of Panax ginseng.

"Baseline" evaluations, PE, history should be completed within 2 weeks prior to registration or 1 week prior to start of study drug(Table 3). The Drug compliance will be monitored with a pill diary and with weekly calls/ or in person meeting the patient by RN along with Toxicity evaluation (See Table 3). Toxicity evaluation, symptom assessment and medication review will include assessment toxicity using NCI CTCAE V4 criteria on Days 8, 15, 21, 29, 36, 43, and 57 (Table 3) (all +/- 3 days). Adverse events (including event name, grade, start/stop date and attribution) will be entered into PDMS/CORe, which will serve as the source documentation for adverse events. The Principal Investigator or physician designee will verify the attribution assigned in PDMS/CORe by signing the PDMS/CORe adverse events printout at the end of protocol treatment. PDMS/CORe will be used as the electronic case report form for this protocol. The unused drug returned will be documented in the shadow chart and destroyed as per institutional policy.

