Global Symptom Evaluation. This instrument is to estimate the minimal important difference in symptoms before treatment and after treatment. Patients will be asked about their symptoms (worse, about the same, or better) after starting new medication. If their answer is better, patients will be asked to rate how much better their symptoms are (almost the same, hardly any better at all, a little better, somewhat better, moderately better, a good deal better, a great deal better, a very great deal better). If their answer is worse, patients will be asked to rate how much worse their symptoms are (almost the same, hardly worse, a good deal worse, a great deal worse, a very great deal worse, somewhat worse, moderately worse, a good deal worse, a great deal worse, a very great deal worse). This evaluation will be performed on day 29 and day 57. **Toxicity Evaluation.** On Day 29, the study will be completed and patients will be given the option of continuing on an open label basis, Panax ginseng 800 mg per day, will be provided they have tolerated the double-blind phase without moderate to severe toxicity as per NCI CTCAE V4 criteria. Toxicities will be evaluated using the NCI CTCAE Version 4 Criteria (Appendix A) on Days 8, 15, 21, 29, 36, 43 and 57 (all +/- 3 days). Adverse event (including event name, grade, start/stop date and attribution) will be documented in the medical record and entered into PDMS/CORe. PDMS/CORe will be used as the electronic case report form for this protocol.

The Investigator or physician designee is responsible for verifying and providing source documentation for all adverse events and assigning the attribution for each event for all subjects enrolled on the trial

C.8 Serious Adverse Events Reporting

An adverse event or suspected adverse reaction is considered "serious" if, in the view of either the investigator or the sponsor, it results in any of the following outcomes:

• Death

• A life-threatening adverse drug experience – any adverse experience that places the patient, in the view of the initial reporter, at immediate risk of death from the adverse experience as it occurred. It does not include an adverse experience that, had it occurred in a more severe form, might have caused death.

- Inpatient hospitalization or prolongation of existing hospitalization
- A persistent or significant incapacity or substantial disruption of the ability to conduct normal life functions.
- A congenital anomaly/birth defect.

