Secondary Analyses: We will compare the physical activity levels of participants in the two groups as measured by the hand grip dynamometer. We will also test the quality of life variables with the HADS and FACT-G tests. As each of these variables is also continuous and measured at the same points in time, we will determine the relationship of each of these variables to fatigue and analyze the data using repeated measures analyses as described above, testing for differences between groups, over time, and a time by group interaction. If several variables appear to be significantly related to fatigue, we will also perform multivariate analyses to determine the best predictors of fatigue as measured by the FACIT-F subscale. We will also determine relationships between daily or weekly fatigue, symptom data, and daily measures of sleep duration and fragmentation by determining correlation coefficients within time periods. Exploratory analyses of all subscale scores will be performed after the primary endpoint has been analyzed.

Summary information on the global symptom evaluation by group will also be provided at each of the assessed time points. Differences in distributions between groups will be analyzed using a chi-square analysis.

On an exploratory basis, we will also investigate whether or not different results were found for patients with different types of cancer, primarily using descriptive statistics. We do not expect to find statistical significance due to the low numbers of patients in each cancer type, but if we do find trends that appear to be significant, we will use this information to inform a future study. Additionally as a part of exploratory analysis, we will use Pearson chi-squared tests to compare the proportion of patients experiencing clinical benefit between each arm.

Information about toxic effects and tolerability will be summarized at each dose level. Safety assessments including hematology and chemistry assessments and toxicity evaluations will be made throughout the study (see Table 3).

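### The Global Symptom Evaluation is an ordered rating, but the arms are to be compared with an unspecified chi-square; in its ordinary form this ignores the order, and the categories are not stated.

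*Combined protocol and SAP*

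**What the plan says.** Section C.7.2.1 (Outcome Measures, Global Symptom Evaluation) describes a two-step rating. First: "Patients will be asked about their symptoms (worse, about the same, or better) after starting new medication". Those who improved then give a degree: "patients will be asked to rate how much better their symptoms are (almost the same, hardly any better at all, a little better", and so on up to the largest improvement. A similar list covers worsening. As printed, that list has ten labels, of which three are repeats, and they are out of order. The stated purpose is: "This instrument is to estimate the minimal important difference in symptoms before treatment and after treatment". On timing: "This evaluation will be performed on day 29 and day 57".

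Section C.9 (Secondary Analyses) gives the whole GSE analysis for the randomised phase in two sentences: "Summary information on the global symptom evaluation by group will also be provided at each of the assessed time points", followed by "Differences in distributions between groups will be analyzed using a chi-square analysis". The same section is more specific about the binary clinical-benefit endpoint: "we will use Pearson chi-squared tests to compare the proportion of patients experiencing clinical benefit between each arm".

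Section C.6.2 says what happens after Day 29 to patients who tolerated treatment: "patients will be given the option of continuing on an open label basis".

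**The concern.** A GSE answer carries direction. A chi-square comparison of distributions, in its ordinary Pearson form, gives the same result however the categories are ordered. It spreads its sensitivity over every possible pattern of difference instead of concentrating on a shift towards better or towards worse. If ginseng moves patient-rated change in one direction, which is the hypothesis of the trial, that sensitivity is partly wasted.

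The categories are also open. Three first-step answers, better versus not better, and the full graded scale all fit the text, and their power differs. Left undecided, the choice could be made after the data are seen.

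Little rests on the result: the GSE is listed under Exploratory Objectives (A.2), and no sizing, stopping, safety or primary decision uses it. However, Section D.10 says that trends on the secondary objectives will feed larger trials and grant applications. A directional signal missed here weakens that use.

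**Working it through.** **1. Does another section supply an ordinal comparison of arms?** No.
- The nonparametric fallback in C.9 is limited to continuous variables.
- The Pilot Analysis lists the GSE among outcomes for paired t or Wilcoxon tests, but that phase has a single arm.
- The repeated-measures plan in Secondary Analyses follows the HADS, FACT-G and hand-grip measures, described as continuous and measured at common time points. The GSE has no baseline or Day 15 value (Table 3).

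**2. The plan's own sizing figure.** Nothing is stated for the GSE. For FACIT-F, Power Considerations gives 50 evaluable per arm, SD 5.8, two-sided 0.05 and 80% power. The detectable difference is (1.960 + 0.842) × 5.8 × √(2/50) = 2.802 × 5.8 × 0.2 = 3.25 points, or 3.28 with the t distribution. The stated 3.3 is reproduced.

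**3. Assumptions for the GSE.**
- Effect: 3.3/5.8 = 0.57 SD, with a range of 0.35 to 0.70 SD.
- Underlying normal response, cut so that placebo answers split worse/same/better as 20/30/50, 25/35/40 or 33/33/33%.
- 50 per arm, two-sided 0.05, 10,000 simulated trials per setting (simulation error about one percentage point).

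**4. One case by hand.** Take placebo 20/30/50%. A shift of 0.57 SD gives 7.9/20.6/71.5% on ginseng. The chi-square noncentrality is n × Σ(p₁ − p₀)²/(p₁ + p₀) = 50 × (0.121²/0.279 + 0.094²/0.506 + 0.215²/1.215) = 50 × (0.0525 + 0.0175 + 0.0380) = 5.4. With 2 degrees of freedom this gives about 54% power, in line with the simulation below.

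**5. Same three levels, with order ignored or used (ranges over the three placebo splits).**

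| Shift (SD) | Chi-square | Wilcoxon | Relative loss |
|---|---|---|---|
| 0.35 | 25–27% | 31–35% | about 21–23% |
| 0.57 | 53–60% | 64–70% | about 14–17% |
| 0.70 | 72–79% | 81–86% | about 9–11% |

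With no effect, both tests reject close to 5% of the time (chi-square 4.9–5.4%, Wilcoxon 4.7–5.2%).

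**6. In patients.** With 64 per arm, the three-level chi-square reaches 66–71%, about what Wilcoxon reaches with 50. As a check, when the effect lies along the order, a 2-df test needs a noncentrality of 9.63 for 80% power, against 7.85 for a 1-df test (ratio 1.23). At 65% power the values are 6.92 and 5.50 (ratio 1.26). 50 × 1.26 = 63.

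**7. Other readings of the categories, at 0.57 SD and 50 per arm.**
- Better versus not better, chi-square: 61–64%. With two categories there is no order left to ignore.
- Graded scale, Wilcoxon: 77–78%. The gain over 64–70% comes from keeping the degrees, not from using order.
- All graded levels in one unordered table: 24–26%, with expected counts below 5 in 80–90% of cells. This needs about 16 levels (7 distinct worse + 1 same + 8 better), which is a reconstruction.

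**8. A second model.** Under proportional odds with placebo 25/35/40% and odds ratios of 2, 2.5 and 3, the three-level chi-square has 35%, 55% and 69% power. A 1-df trend chi-square has 44%, 64% and 79%. The gap is again about 10 points.

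**The case against.** The strongest reply is that no error is shown. The ordinary chi-square holds its level, and the plan asks about differences in distributions, which is the question that test answers. The wording does not exclude a trend form, and since the authors wrote Pearson for clinical benefit, its absence here could mean something else. If better versus not better is tested, the charge of ignoring order falls away. The GSE is exploratory, its stated purpose is to help estimate a minimal important difference, and the frequencies by arm will be visible whatever the p-value. The absolute powers rest on an effect borrowed from another scale and on assumed placebo shares, in a pure-shift setting that favours a rank test.

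Much of this stands. The test is valid, the loss from ignoring order is conditional on the ordinary form being used, and the absolute powers illustrate the point but are not properties of the plan. The 16-level figure should carry no weight, because no section proposes that table. An ordinal test also has a real blind spot. With no shift but a spread 1.5 times as wide in one arm, three-level chi-square has 16–19% power, against about 5% for Wilcoxon on the graded scale.

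The reply does not remove the gap. Neither form nor categories are fixed, and the default reading gives up sensitivity to the directional effect the trial looks for. The gap of about 10 points on three levels appears under both models.

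**Conclusion.** The concern holds, as a minor point. The plan's only between-arm test for an ordered outcome is a chi-square of unstated form on unstated categories. Read in the ordinary way on three levels, it loses about 14–17% of the power available from the same data (53–60% against 64–70%), equivalent to needing about 64 instead of 50 patients per arm. The relative loss ranges from about 9–11% at 0.70 SD to about 21–23% at 0.35 SD. These sizes assume a one-directional shift, an effect borrowed from FACIT-F and assumed placebo distributions. The direction of the loss did not change across the shifts, placebo splits and models tried. The primary analysis, sample size, safety monitoring and error rate of the trial are unaffected.

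**What to change.** In Section C.9 (Secondary Analyses), before unblinding:

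- Code the GSE as one ordered scale, from the greatest worsening through no change to the greatest improvement. Confirm the options against the actual form, since the printed list for worsening repeats labels out of order.
- Compare arms at Day 29 with one named ordinal method: a Wilcoxon rank-sum test, or a proportional-odds model if an effect estimate is wanted.
- Keep the frequency table by arm. It would show a polarised pattern that the ordinal test can miss.
- Report Day 57 descriptively by randomised arm. Continuing patients from both arms are then on open-label ginseng, so a comparison at that visit is no longer ginseng against placebo.

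The cost is one or two sentences, with no extra data or patients. The price is lower sensitivity to a difference in spread without a shift.
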